9.1.7 Withdrawal Criteria

The subjects who meet the criteria listed in Subject Withdrawal Criteria section will be discontinued from treatment or they may can choose to withdraw voluntarily at any time. Subjects may be withdrawn if the investigator deems that it is detrimental or risky for the subject to continue. All withdrawn subjects should attend the final study visit. Withdrawn subjects after randomization will not be replaced and will be followed for outcomes.

Subject Withdrawal Criteria

9.1.7.1 Patients with exacerbation which is not controlled by per protocol rescue medicine in 2 weeks.

9.1.7.2 Infection failed to be treated with per protocol oral antibiotic. Or those who develop cutaneous sepsis, as defined by skin infection + >/= 2 meets SIRS definition, as defined below:

9.1.7.2.1 Temp >38.5°C or > 36°C.

- 9.1.7.2.2 Tachycardia or bradycardia (if <1 year).
- 9.1.7.2.3 Tachypnea or requiring mechanical ventilation.
- 9.1.7.2.4 Abnormal leukocyte count or >10% bands.
- 9.1.7.3 Infection which are not deemed related to atopic eczema <i.e pneumonia, UTI, AGE, will not be withdrawn even if fulfilled sepsis criteria.
- 9.1.7.4 The development of any severe adverse event, as defined by the Malaysian GCP.
- 9.1.7.5 Use of any forbidden medication or treatment, and/or other use moisturisers or emollients during the trial that could affect the study result.
- 9.1.7.6 Subjects who did not comply with the protocol of at least two times-per-day application of cream.
- 9.1.7.7 Subject's withdrawal of consent.
- 9.1.7.8 Detection of eligibility violations, occurrence of other significant protocol violations during the trial.
- 9.1.7.9 Investigator's decision to terminate the process for the sake of the subject's health.
- 9.1.7.10 Dropouts are defined as patients who did not attend for follow-up visit within the designated visit window (+/- 3 days) and whose outcomes are unknown by the end of the trial.

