9.1.10 Study Visits and Procedures

- 9.1.10.1 Subjects who are eligible to take part in this trial will need to attend to the study site for a total of 5 compulsory visits, as illustrated in Fig. 3.
- 9.1.10.2 During the screening/baseline visit, it will take about 1 hours where the investigators will take note of the subjects conditions for evaluation of study acceptability.
- 9.1.10.3 Prior to any baseline measurement, the correct usage of the cream will be explained by the investigator and the investigator's team. Subjects will be required to apply at least 1 fingertip unit to 2% body surface area. The subjects will receive treatment with the IP for topical application for 3 times a day for 12 weeks (according to the guideline that emphasize the important of using sufficient emollient).
- 9.1.10.4 Subjects will be provided with non-soap-based shower product (REMDII® Calming Body Wash, Malaysia) for subject's shower purpose throughout

the study. Subjects should avoid the usage of soap-based products throughout the study.

- 9.1.10.5 Subjects will also be provided with a diary, for recording of any application of rescue treatment and deviation from the study protocols.
- 9.1.10.6 Subjects who have flare up, will be managed using hydrocortisone 1% cream for a duration of 7 days. Those who are not responding to hydrocortisone end of 7 days will be prescribed with clobetasone butyrate 0.05% cream for additional 7 days. Those who doesn't respond to the treatment shall be withdrawn. However, subjects need to record the application in the provided diary. As well, any deviation or illness that occurs during the study will need to be recorded in the same diary as well.
- 9.1.10.7 Those who acquired secondary bacterial infection will be treated with a week of cloxacillin (50-100mg/kg/day po in 4 divided dose). For those who are above 20kg, will receive the usual adult dose.
- 9.1.10.8 In patients with penicillin allergy will be given a week of erythromycin ethylsuccinate at a dose of 30mg/kg/day in divided dose (up to a max 2gm/day).
- 9.1.10.9 Patients who have eczema herpeticum will received a week of oral acyclovir, in which subjects 1 month till 2 years will receive 100mg 5×/day; while subjects age 2 to 12 years old will received 200mg 5×/day dosage.
- 9.1.10.10After the explanation of the "Dos and Don'ts" to the guardians/parents, baseline measurement of atopic dermatitis severity of subjects using SCORAD index will be conducted.

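### The temperature limit in the cutaneous sepsis withdrawal rule (9.1.7.2.1) reduces to any temperature above 36°C, so normal temperature counts as a sepsis sign and low temperature never does

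*Protocol*

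**What the plan says.** Section 9.1.7 of the Protocol makes its withdrawal list binding: "The subjects who meet the criteria listed in Subject Withdrawal Criteria section will be discontinued from treatment". Item 9.1.7.2 gives two infection-related grounds: failure of the protocol's oral antibiotic, or cutaneous sepsis. The second is worded "Or those who develop cutaneous sepsis, as defined by skin infection + >/= 2 meets SIRS definition, as defined below".

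Four signs follow:

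- 9.1.7.2.1, temperature: "Temp >38.5°C or > 36°C"
- 9.1.7.2.2, heart rate: "Tachycardia or bradycardia (if <1 year" (closing bracket follows)
- 9.1.7.2.3, respiration: "Tachypnea or requiring mechanical ventilation"
- 9.1.7.2.4, white cells: "Abnormal leukocyte count or >10% bands"

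A skin infection without sepsis is managed within the trial. Section 9.1.10.7 states: "Those who acquired secondary bacterial infection will be treated with a week of cloxacillin". No other section restates or corrects the temperature limit.

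**The concern.** Two bounds joined by *or* are informative only if they point in opposite directions. Here both point upward, so the lower one absorbs the higher and the 38.5°C limit does nothing. Normal body temperature becomes a sign of sepsis, and hypothermia, which the second bound was presumably meant to catch, is left out.

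The error acts in both directions. A child at normal temperature with a skin infection and one other sign must be taken off the product on the strength of a sign that is not abnormal. Without that sign the child would stay on the product, receive the week of antibiotic under 9.1.10.7, and be withdrawn only if it failed or sepsis developed. Conversely, a cold child with one other sign is not caught by the mandatory rule. The trial enrols from 1 month of age, so a temperature rule that protects participants should be correct as printed.

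**Working it through.** **Inputs** (all from section 9.1.7): the temperature item as printed; three other signs; skin infection present; withdrawal when at least 2 of the 4 signs are present. The protocol offers no figure of its own to reproduce on this point.

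**Step 1: reduce the temperature item.** Let T be temperature in °C.

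{T > 38.5} or {T > 36} = {T > 36}

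because the first set lies inside the second. A check from 33.0 to 42.0°C in steps of 0.1°C gave the same answer for both forms at every value.

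**Step 2: count the further signs needed.** If the temperature item is met, 2 − 1 = 1 further sign is enough. If not, 2 are needed. The comparison version, T > 38.5 or T < 36, is an assumption about intent.

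| Temperature | Further signs needed, as printed | Further signs needed, with T < 36 |
|---|---|---|
| below 36°C | 2 | 1 |
| exactly 36°C | 2 | 2 |
| above 36°C, up to and including 38.5°C | 1 | 2 |
| above 38.5°C | 1 | 1 |

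**Step 3: count patterns.** Three other signs, each present or absent, give 2³ = 8 patterns: 1 with none, 3 with exactly one, 3 with exactly two, 1 with all three.

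- Temperature item met (at least 1 other sign needed): 3 + 3 + 1 = 7 of 8 lead to withdrawal.
- Temperature item not met (at least 2 other signs needed): 3 + 1 = 4 of 8 lead to withdrawal.

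| T (°C) | As printed | With T < 36 |
|---|---|---|
| 35.5 | 4 of 8 | 7 of 8 |
| 36.0 | 4 of 8 | 4 of 8 |
| 37.0 | 7 of 8 | 4 of 8 |
| 38.5 | 7 of 8 | 4 of 8 |
| 39.0 | 7 of 8 | 7 of 8 |

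Wherever the two rules disagree, the gap is 7 − 4 = 3 patterns, namely those with exactly one other sign. The patterns are not equally likely, so these counts describe the logic of the rule and not how often it will misfire.

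**The case against.** The strongest reply is that this is an obvious slip. The item stands under a SIRS heading, and a physician is unlikely to treat normal temperature as a sign of sepsis, so few children, perhaps none, would be withdrawn wrongly. That may well be how it plays out. But an investigator who spots the slip must then depart from a mandatory written rule, and one who does not spot it applies a wrong one.

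A fault in reading the PDF cannot be wholly excluded: item 9.1.7.3 contains a stray, unclosed angle bracket, so symbols in this list are not perfectly reliable. Against that, the less-than sign survives in the very next item, 9.1.7.2.2. A misread character is possible but speculative.

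Several points limit the consequence, and they stand:

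- The temperature item alone withdraws nobody, and the two readings part only when exactly one other sign is present.
- Under either reading, sepsis leads to withdrawal without waiting for the antibiotic to fail. The complaint is only that the printed rule labels too many children septic. Nothing in the protocol says that stopping the moisturiser denies a child antibiotics.
- The white-cell sign needs a blood count, which is not among the visit procedures in 9.1.10, so some patterns may seldom be observed.
- Investigator discretion (opening of 9.1.7, and 9.1.7.9) can cover the cold child. It allows extra withdrawals, however, and cannot cancel one that the text requires.
- Section 9.1.7 has withdrawn children attend the final visit and be followed for outcomes, so their data need not be lost.
- Active secondary infection is an exclusion at entry (9.1.6.3), and only 33 children are planned.

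Together these bear on how often the error would bite. None makes the rule correct.

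**Conclusion.** The point holds. As printed, 9.1.7.2.1 is equivalent to T > 36°C, and this follows from the text alone. For a child with a skin infection, the number of further signs needed falls from 2 to 1 above 36°C and up to 38.5°C, and rises from 1 to 2 below 36°C, compared with a rule whose lower limit is below 36°C. That comparison assumes the intended limit, which the investigators must confirm.

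The protocol gives no frequency of skin infection with SIRS signs, so no number of affected children can be stated. Significance level, power and sample size are untouched, and no effect on the endpoint analysis is claimed. It should still be fixed: a mandatory discontinuation threshold in a paediatric trial is wrong as written, and the correction is trivial.

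**What to change.** Reverse the second inequality in 9.1.7.2.1 so that the item reads as a temperature above 38.5°C or below 36°C, after the investigators have confirmed both limits against the SIRS definition they meant to use. Check the protocol's source file at the same time to rule out a display fault.

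The cost is a one-character correction, notified to the ethics committee. There is no change to visits, sample size or analysis.

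If the section is opened anyway, one optional sentence could say whether 9.1.7.3, which keeps children with infections unrelated to eczema in the study, takes precedence over 9.1.7.4 on severe adverse events. The main correction does not depend on it.

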9.1.8 Sample Size

Sample size calculations were performed according to Cheon et al. (2013) using the following formula, where the mean difference and standard deviation of the scoring atopic dermatitis (SCORAD) index will be 10 and 13.576, respectively.

$$n = \frac{2(z_{\alpha/2} + z_{\beta})^2 \sigma^2}{(\mu_c - \mu_t)^2} = \frac{2 \times (1.96 + 0.84)^2 \times 13.576^2}{10^2} = 28.932$$

Using 80% power, a 5% significance level, and a 10% dropout rate, the required sample size will be corrected to approximately 33 participants for a group. Therefore, a total of 33 participants will be needed for this trial.

9.1.9 Study Duration and Timeline

Stage 1, review of medical records – 0.5 months
Stage 2, data collection and data analysis – 1-12 months
Stage 3, presentation and publication - 6-18 months

The participation duration for each subject is 3 months.

9.1.10 Study Visits and Procedures

- 9.1.10.1 Subjects who are eligible to take part in this trial will need to attend to the study site for a total of 5 compulsory visits, as illustrated in Fig. 3.
- 9.1.10.2 During the screening/baseline visit, it will take about 1 hours where the investigators will take note of the subjects conditions for evaluation of study acceptability.
- 9.1.10.3 Prior to any baseline measurement, the correct usage of the cream will be explained by the investigator and the investigator's team. Subjects will be required to apply at least 1 fingertip unit to 2% body surface area. The subjects will receive treatment with the IP for topical application for 3 times a day for 12 weeks (according to the guideline that emphasize the important of using sufficient emollient).
- 9.1.10.4 Subjects will be provided with non-soap-based shower product (REMDII® Calming Body Wash, Malaysia) for subject's shower purpose throughout

the study. Subjects should avoid the usage of soap-based products throughout the study.

- 9.1.10.5 Subjects will also be provided with a diary, for recording of any application of rescue treatment and deviation from the study protocols.
- 9.1.10.6 Subjects who have flare up, will be managed using hydrocortisone 1% cream for a duration of 7 days. Those who are not responding to hydrocortisone end of 7 days will be prescribed with clobetasone butyrate 0.05% cream for additional 7 days. Those who doesn't respond to the treatment shall be withdrawn. However, subjects need to record the application in the provided diary. As well, any deviation or illness that occurs during the study will need to be recorded in the same diary as well.
- 9.1.10.7 Those who acquired secondary bacterial infection will be treated with a week of cloxacillin (50-100mg/kg/day po in 4 divided dose). For those who are above 20kg, will receive the usual adult dose.
- 9.1.10.8 In patients with penicillin allergy will be given a week of erythromycin ethylsuccinate at a dose of 30mg/kg/day in divided dose (up to a max 2gm/day).
- 9.1.10.9 Patients who have eczema herpeticum will received a week of oral acyclovir, in which subjects 1 month till 2 years will receive 100mg 5×/day; while subjects age 2 to 12 years old will received 200mg 5×/day dosage.
- 9.1.10.10After the explanation of the "Dos and Don'ts" to the guardians/parents, baseline measurement of atopic dermatitis severity of subjects using SCORAD index will be conducted.
- 9.1.10.11Initial weight of cream provided to subjects will be recorded and weighed.
- 9.1.10.12Subjects will be required to pay their visit to the study site, as stipulated, which takes about 45 minutes for each visit.
- 9.1.10.13Measurement of atopic dermatitis severity using IGA and SCORAD index will be conducted. DLQI will be answered by subjects at each visit too.
- 9.1.10.14Measurement of high resolution ultrasound skin-imaging (HR-USI), skin color and transepidermal water loss (TEWL) will be conducted using DermaLab® Series SkinLab Combo (DermaLab®, Denmark).

- 9.1.10.15Subjects need to submit the old bottles of cream to investigator where they will be weighed in every visits. New cream will be provided to subjects, when necessary, in which the weight will be recorded too.
- 9.1.10.16Subjects also have to submit their diaries to investigator. New sets of diaries will be provided to subjects.
- 9.1.10.17All adverse events that happened throughout the study will be recorded.

9.2 Risk and benefit to study participants

Tocotrienol rich composition used in the topical is GRAS. As stated in the literature above, there are no adverse effects known to be caused by the IP. REMDII[®] Sensitive has been registered to the National Pharmaceutical Regulatory Agency (NPRA), Kementerian Kesihatan Malaysia with the notification number NOT181000506K and certified halal. All topicals shall expect to have irritation, burning, stinging sensation and folliculitis. There is low risk of sensitization to the topical ingredients. The study procedures are all routine procedures for the disease/condition studied. There is thus minimal risk for subjects. All parties will be insured by trial insurance paid for by the sponsor.

9.2.1 Potential benefits

- All subjects will be provided with free moisturisers and gentle body cleanser (REMDII®, Malaysia) for 3 months.
- Each subjects will be provided with an emolument of RM30/visit which will cover for their transportation. F & B will be provided at site.
- Access to promising new treatments often not available outside the clinical-trial setting.
- Treatment that may be more effective than the standard approach, Vitamin E has been tested to be safe and without known negative side effects.
- Close monitoring, advice, care, and support by a research team of doctors and other health care professionals who understand your disease or condition, free of charge.
- The opportunity to be the first to benefit from a new method under study.

- The chance to play an active role in your own health care and gain a greater understanding of your disease or condition.
- The chance to help society by contributing to medical research. Even if you don't directly benefit from the results of the clinical trial you take part in, the information gathered can help others and adds to scientific knowledge. People who take part in clinical trials are vital to the process of improving medical care.

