The IP of this study is a topical moisturiser containing tocotrienol rich composition from plant source (REMDII[®] Sensitive, Malaysia). REMDII[®] Sensitive contains both tocopherol (α , β , $\gamma \& \delta$) and tocotrienol (α , β , $\gamma \& \delta$). Serbinova, Kagan, Han, and Packer (1991) showed that tocotrienols can be 40-60 times more potent as antioxidant than tocopherols. Vitamin E especially palm-based has been proven repeated to exhibit no adverse effects in both normal as well as vulnerable subjects while potentially poses significantly high benefits with very low risks (Argyriou et al., 2006; Kappus & Diplock, 1992; Meydani et al., 1998). In a prospective, randomised, double-blinded trial involving 84 post-surgical subjects, no significant adverse effect was observed up to the dosage of 5% topical tocotrienol, applied twice-daily over 4 months post-surgery (Khoo et al., 2011). In another study, Hasan, Idris, Gani, and Basri (2018) concluded that palm tocotrienol rich fraction has no indication of irritancy to both ocular and dermal tissues and could be

classified as Category 1 according to United Nations Globally Harmonised System of Classification and labelling of Chemicals. Hasan, Ismail, and Ahmad (2008) also concluded that palm tocotrienol rich fraction do not induce any cutaneous reactions including irritation and dermatitis and it is safe to be used for topical applications. REMDII[®] Sensitive has been registered to the National Pharmaceutical Regulatory Agency (NPRA), Kementerian Kesihatan Malaysia with the notification number NOT181000506K, tested for its product stability and certified halal. Thus, subject could benefits freedom of better accessibility to the Vitamin E in the IP with lesser risk on exposure to unknown degradatory products resulted from product instability. Besides, REMDII[®] Sensitive has also been tested to have low risk of adverse effect ($LC_{50} = >5000$ $\mu g/mL$) in vivo.

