As a topical cosmetic or over-the-counter product, Vitamin E has been used in product concentration of 1%-5% (w/w) for almost half a century. The lipophilic nature of vitamin E makes it suitable for topical application and percutaneous absorption through the skin (Krol, Kramer-Stickland, & Liebler, 2000; Lin et al., 2003). When topically applied, vitamin E has been shown to hydrate the stratum corneum (SC), improve skin hydration and improve water-binding capacity (Ismail, Affandi Yusoff, & Hashim, 2009; Manela-Azulay & Bagatin, 2009). Topical vitamin E was also found to significantly reduced postoperative pain in a prospective randomized clinical trial involving 60 patients (Ruiz-Tovar et al., 2016). Thiele, Hsieh, and Ekanayake-Mudiyanselage (2005) summarised that Vitamin E could be considered an effective ingredient for imparting skin protection and treating atopic dermatitis (AD) based on experimental evidences suggesting that topical and oral vitamin E has anticarcinogenic, photoprotective, and skin barrier-stabilizing properties. In a 2015 randomized, controlled, double-blind, single center study involving 44 patients with mild to moderate AD in the perioral/periocular area and/or the neck, Patrizi et al. (2016) noted a significantly more rapid reduction in affected surface area with an emollient containing Vitamin E, compared with placebo; the product was found to be well tolerated and safe as well as effective for mild to moderate AD. Maarouf, Vaughn, and Shi (2018) also agrees that topical Vitamin E formulations appear to provide some benefit to AD individuals. In addition, Yap (2018) also showed that tocotrienol rich fraction is an effective anti-inflammatory agent that is safe to be applied daily. As nitric oxide (NO) has been shown to be involved in the pathogenesis of vasodilation and erythema in atopic dermatitis (Taniuchi et al., 2001), REMDII[®] Sensitive could be as potential product with potential in the management of AD. REMDII[®] Sensitive is tested to have inhibited ~50% NO level in vivo, slightly lower to ~60% NO inhibition activity of hydrocortisone 1% (w/w) (Hydrocortisone[®] Cream, Xepa-Soul Pattinson) *in vivo* (p>0.05).

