9.1.6 Exclusion Criteria

- **9.1.6.1** Individuals with confounding skin diseases other than atopic dermatitis in the affected area which could interfere with assessment of treatment (e.g. psoriasis, rosacea, erythroderma, ichthyosis, acne, Netherton's syndrome, scabies, seborrheic dermatitis, and cutaneous lymphoma).
- **9.1.6.2** Individuals with severe atopic dermatitis (IGA = 4).
- 9.1.6.3 Individuals with active ongoing secondary infection of atopic dermatitis.
- **9.1.6.4** Individuals with any physical attributes or skin conditions that might interfere with the clear visual or instrumental assessments (i.e. cuts, sunburn, birth marks, tattoos, extensive scarring, excessive hair growth or acne).
- **9.1.6.5** Individuals with diabetes, severe liver disability (2.5-fold the normal high range value for ALT, AST) or severe renal disability (sCr > 2.0 mg/dl).
- **9.1.6.6** Individuals with immunodeficiency disorder or infectious disease (e.g. hepatitis, tuberculosis, HIV or AIDS, lupus rheumatoid arthritis.

- **9.1.6.7** Subjects who are not keen to start on corticosteroid on screening, despite informing that it is the first line treatment option according to the National Atopic Dermatitis guideline.
- **9.1.6.8** Use of other topical or systemic medications that could affect the course of their atopic dermatitis during the study period (except inhaled steroids and/or stable antihistamines for asthma or allergies for the past 30 days).
- **9.1.6.9** Use of steroids, oral antibiotics, immunosuppressants, other systemic treatments (i.e. retinoids, methotrexate, cyclosporine, hydroxycarbamide (hydroxyurea) and azathioprine) or physical therapy (i.e excimer laser, NBUVB, or PUVA) that could affect AD within 30 days or 5 half- lives.
- 9.1.6.10 History of drug abuse.
- **9.1.6.11** Hypersensitivity to Vitamin A, Vitamin C, Vitamin E or oil palm derived products.
- **9.1.6.12** Poorly controlled bronchial asthma, as mentioned according to GINA guideline.
- **9.1.6.13** Individuals with any other condition or factor the Investigator or their duly assigned representative believes may affect the ability of the subject to complete the study or the interpretation.

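### Section 9.2.1 lists superiority and novelty as benefits of taking part, in wording addressed to participants, and the protocol does not support either

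*Protocol*

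**What the plan says.** Section 9.2.1 lists, among the benefits to participants:

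- "Access to promising new treatments often not available outside the clinical-trial setting"
- "Treatment that may be more effective than the standard approach", in a bullet that goes on to say vitamin E has been tested as safe and has no known harmful effects
- "The opportunity to be the first to benefit from a new method under study"

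The section speaks to the participant directly. One bullet, for example, promises support from "health care professionals who understand your disease or condition, free of charge".

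Other parts of the protocol bear on these lines:

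- **Standard treatment.** Criterion 9.1.6.7 excludes families unwilling to start a corticosteroid "despite informing that it is the first line treatment option according to the National Atopic Dermatitis guideline".
- **Comparison with a corticosteroid.** Section 7 says the product "inhibited ~50% NO level in vivo, slightly lower to ~60% NO inhibition activity of hydrocortisone 1% (w/w"), and gives p>0.05.
- **Regulatory status.** Sections 7 and 9.2 say the product "has been registered to the National Pharmaceutical Regulatory Agency (NPRA), Kementerian Kesihatan Malaysia with the notification number" that they then state.
- **Design.** Section 9.1.1 describes one open-label arm.
- **Local reactions.** Section 9.2 expects stinging, burning, irritation and folliculitis with any topical and mentions a low risk of sensitisation. Section 9.2.2 adds allergic reaction.

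**The concern.** A benefit list should state only what the evidence supports. Here parents deciding for infants and young children may be led to think that the cream could outperform standard treatment, that it is new, and that it carries no known side effects. That is a consent problem whatever its effect on the data.

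There is also a measurement problem. Families know what they are using, and several secondary outcomes are their own ratings. Wording that suggests the hoped-for result before any rating is made can shift those ratings. With no control arm, a shift of that kind cannot be separated from an effect of the product.

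**Working it through.** Little arithmetic applies, so the check sets each benefit statement against the rest of the protocol.

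**1. Superiority over standard care.**
- Section 7 reports no clinical comparison of this product with any standard treatment, and it concedes that clinical evidence on tocotrienol in children's skin is sparse.
- The nearest clinical evidence is a cited randomised trial in 44 patients with mild to moderate disease. It compared a different emollient containing vitamin E with placebo, not with standard care.
- The one figure that places the product beside a corticosteroid is nitric oxide inhibition: about 50% for the product and about 60% for hydrocortisone 1%. Difference: 60 − 50 = 10 percentage points in favour of hydrocortisone. Ratio: 50/60 = 0.83. The protocol reports p>0.05 and gives no sample size or interval. This is a surrogate marker. It lends no support to superiority, and it does not establish inferiority.
- The trial cannot supply the missing evidence, because section 9.1.1 has no comparator. Section 11 mentions a vehicle group, but the design contains none.

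**2. Novelty and availability.**
- Sections 7 and 9.2 give a national notification number for the product.
- Section 7 also says that vitamin E has been used in cosmetic or over-the-counter products for close to fifty years.
- Calling the cream a new method, or participants the first to benefit, fits poorly with both statements.

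**3. Side effects.**
- The reassurance in 9.2.1 is about vitamin E, whereas the reactions in 9.2 and 9.2.2 are those of topical products. A parent reading a list of trial benefits would not draw that distinction.
- Section 9.2 is itself uneven: it says no adverse effect of the product is known, then lists reactions to be expected of any topical.

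**4. Which outcomes could be affected.**

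| Outcome | Role (9.1.3) | Who rates it, as stated |
|---|---|---|
| IGA | Primary | Clinician (section 6) |
| SCORAD | Secondary | Clinician (section 6) |
| PO-SCORAD | Secondary | Patient (section 6) |
| Pruritus | Secondary | Carer, for the VAS at entry (9.1.5.3); patients' assessment (section 6) |
| Quality of life | Secondary | Subjects (9.1.10.13) |
| HR-USI, TEWL, skin colour | Secondary | Instrument (9.1.10.14) |

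Expectation among families bears directly on PO-SCORAD, pruritus and quality of life.

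**5. Size.** The protocol contains nothing from which the contribution of this wording could be estimated, so no figure is given.

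**The case against.** The defence has several sound points.

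- **The text hedges.** The superiority line says only that the treatment may be better, and the availability line says often. A non-significant surrogate cannot contradict a statement of possibility. This stands, so the lines are unsupported rather than refuted.
- **The standard approach is not defined.** Section 7 calls corticosteroids and calcineurin inhibitors the standard anti-inflammatory choice, but it also calls moisturisers the safest and most basic therapy. If ordinary emollient care is meant, the hydrocortisone figure is beside the point. Even then, the protocol shows no comparison of this product with another emollient and plans none.
- **What families are told is not shown.** Section 9.2.1 is protocol text. Section 9.2.4 says an information sheet is provided and explained, but that sheet is not available here. The second-person wording makes reuse likely without proving it.
- **There is balancing text.** Section 9.2.1 allows that a participant may not benefit directly, 9.2.2 lists risks, and 9.1.6.7 has families told that corticosteroid is first-line. This softens the impression but does not supply evidence for the superiority line.
- **Notification is not sale.** The protocol does not say that the product is on the market. A reader might infer that the protocol claims the cream cannot be had elsewhere, or that it demonstrably can. It says neither.

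A reader might also infer that carers would be slower to report a flare or to ask for rescue. No passage supports this. Criterion 9.1.5.5 requires that there be no objection to topical corticosteroids, and 9.1.10.5 and 9.1.10.6 require rescue use to be recorded in the diary.

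**Conclusion.** The point holds as one about unsupported wording. The superiority and novelty lines in 9.2.1 have no basis elsewhere in the protocol, and the safety statement in the same bullet does not agree with 9.2 and 9.2.2. The effect on consent, and any expectation bias in PO-SCORAD, pruritus and quality of life, depends on an assumption: that the text, or something like it, reaches families before they rate outcomes.

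The bias is of unknown size. It would be tempting to put an assumed shift through a power calculation and quote the resulting false-positive rate. That would describe an uncontrolled shift from any source in a single-arm open-label trial, not the part due to these lines, and most of it could remain after they were removed. It would also be wrong to conclude that the primary analysis is compromised by this wording, since IGA is described as clinician-assessed. The sample size in 9.1.8 is not involved.

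This is a modest point, worth acting on because the correction is cheap and makes the information for parents accurate.

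**What to change.** Delete or neutralise the three lines in 9.2.1, and do the same in any advertisement, briefing text or information sheet built on them. Neutral replacement text would say that the product is a notified moisturiser, that it is not known whether it improves eczema, and that the trial does not compare it with standard treatment. Bring the side-effect statement in 9.2.1, and the matching sentence in 9.2, into line with the local and allergic reactions that 9.2 and 9.2.2 already list.

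The cost is a text edit, an ethics notification and slightly less attractive recruitment material. No visit, endpoint, analysis or sample size changes. The edit removes one avoidable source of expectation; it does not make up for the lack of a control arm.
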